However, the effective modulation of brain activity may depend not on the absolute current density, but on the current flow that is normal to the cortical surface. This is because the neurons of the cortex are aligned perpendicular to the cortical surface, and the induced current serves to alter neuronal polarization along the apical dendrite to somatic axis of the cortical pyramidal neurons (Datta, Zhou, Su, Parra, & Bikson, 2013). Wagner et al (2004) point out that as little as 30% of the current induced by TMS may be oriented normal to the cortical surface. This implies that TEN, which can be directed from the 256 channel array to be oriented mostly normal to the cortical surface, may achieve effective dosage that is within a factor of 10 less than the magnitude of the effective TMS induced current.

Importantly, a major advantage of TEN over TMS is the ability to reach deep sources. In the simulations of TMS by Wagner, et al. (2004), the depth penetration of TMS was 2 cm into brain tissue, where it reached only the crown of the gyrus, and there the current was largely tangential to the gyral crown (rather than surface normal). We must assume, therefore, that the targeting in the existing studies of slow rTMS for epilepsy (Fregni, et al., 2006; Sun, et al., 2012) was highly approximate. Although Fregni et al. used focal cortical dysplasias to guide targeting, it is highly unlikely that these were all within 2 cm of the cortex, or that effective targeting of current direction was achieved.

Therefore, considering these several factors, we can reasonably expect that the electrical dosage of the GTEN 100, with the safety and comfort level set at $200 \mu\text{A}$ per electrode for the study protocol pulses (**Figure 10**), when targeted appropriately to the epileptogenic focus with the 256 array and the high resolution head model, will be an effective treatment for seizure suppression.

Clinical Feasibility Trial Design

The goal of this unblinded and uncontrolled (“open-label”) feasibility study is to evaluate the safety, comfort, and preliminary efficacy of GTEN 100 treatment in achieving temporary suppression of epileptic activity, as assessed primarily by spikes and secondarily by seizures. The GTEN 100 applies small, electrical currents (up to $200 \mu\text{A}$ per electrode and up to 2 mA total) in a pattern that targets the cortical site of epileptiform discharges in order to decrease the excitability of the epileptogenic cortical tissue.

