The primary endpoint is a temporary suppression of epileptic spikes. With assessments of spike rates at weeks 2, 4, 8, 16, and 24, the study will allow estimation of how temporary a suppression is achieved by the one-week treatment. The routine dEEG sessions typically collect dEEG for over an hour, and spike rates per hour will be the standard metric. To be successful, and to warrant progression to a randomized clinical trial, this clinical feasibility study must demonstrate successful targeting and suppression of the epileptogenic zone, as evidenced by temporary but statistically significant spike suppression in contrast to the pre-treatment baseline. All spike rates (baseline, treatment, and follow-up) will be counted as spikes per hour and classified in relation to waking or sleep stage (N1, N2, N3).

Secondary Endpoints and Study Success

The secondary endpoint is monthly suppression of seizures, assessed by the seizure diary each month for six months following treatment, in comparison to the mean seizure frequency for the one-month pre-treatment evaluation baseline. It is clearly advantageous if there is seizure as well as spike suppression as we plan the design of the pivotal trial.

Additional secondary endpoints will be (1) any improvement of cognitive function testing beyond the practice effect (estimated from norms and the improvement in the sham control group); (2) any improvement in quality of life ratings.

Study Monitoring Committee

The safety and comfort decisions for each patient are made by the epileptologist at each site. The safety, comfort, and efficacy of each treatment protocol across sites are reviewed by the Study Monitoring Committee. Vigilance will be maintained throughout the pivotal study to insure safety (no provoked seizures and no adverse effect to non target brain regions). Treatment will be discontinued for any patient that shows treatment-induced seizures, defined as seizures that are not the patient's typical seizures or that occur twice as frequently as the patient's typical seizures, as assessed during baseline. If there are more than five patients with worsening seizures (meeting escape criteria as stated above), the treatment will be suspended at that site. The Study Monitoring Committee (and the FDA when possible) will decide if the trial with that treatment should be terminated at all sites.

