The dEEG is reviewed after each treatment and follow up session, by visual inspection by a trained electroencephalographer and with an automated spike detection and clustering algorithm (EGI's Spike Beacon software), with the quantitation reported as a trial endpoint. If there is an apparent change in the spike (and possibly seizure) localization, as indicated by the spike topography clustering, Electrical Source Imaging is conducted with GeoSource to determine if there is a change in localization. If there is a change in localization, or if there is an increase in spike frequency of over one standard deviation compared to the baseline sessions, or if there is non typical seizure activity, the results are conveyed to the epileptologist supervising the clinical trial to evaluate the risk for the patient's continuation of the trial.

The experimental procedures for each patient session are summarized in Table 2.

Monitoring of Risk

A daily diary with a count and description of seizures is reviewed at each session (treatment and follow up). If there is an increase in seizures of two-fold over the patient's baseline levels, the patient's treatment is suspended and the safety of the treatment is evaluated by the epileptologist, patient, and family. In the follow up sessions, routine dEEG evaluations, cognitive function assessments, and quality of life ratings are conducted once each week for three weeks following the treatment, and then week 8. At each follow up session, cognitive function is assessed with the California Verbal Learning Test, a widely used and easily administered test (www.pearsonclinical.com), and quality of life is assessed with the Quality of Life In Epilepsy Questionnaire (http://www.rand.org/health/surveys_tools/qolie.html).

Overview of Study Protocol

Table 2 presents an overview of the treatment protocol. An exception is that for the first ten patients the dEEG will be monitored for seizures for 3 hours after the first treatment session.

Session	Procedure
Pre-Treatment Evaluation	Review of seizure diary each week for one month. Two routine dEEG evaluations to capture epileptiform discharges (ED), including spikes and seizures. MRI when available to determine possible malformations of cortical development and build individual head model.

Session	Procedure

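### The protocol does not say whether the visual or the automated spike count is the primary endpoint and describes no masked reading, so an uncontrolled pre-post success rule is open to reading drift and choice of count.

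*Protocol*

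**What the plan says.** Under Review of the EEG for Safety and for Spike Counts, the protocol states: "The dEEG is reviewed after each treatment and follow up session". The review is done "by visual inspection by a trained electroencephalographer and with an automated spike detection and clustering algorithm" (the sponsor's Spike Beacon software), "with the quantitation reported as a trial endpoint". The sentence does not say which of the two readings supplies the endpoint, or what happens if they disagree.

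Under Primary Endpoint and Study Success: "The primary endpoint is a temporary suppression of epileptic spikes". Rates from all three phases (baseline, treatment and follow-up) "will be counted as spikes per hour and classified in relation to waking or sleep stage". The unit is therefore common to all phases, but no counting method, reader or software setting is named. Success, and progression to a randomized trial, requires "temporary but statistically significant spike suppression in contrast to the pre-treatment baseline".

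Clinical Feasibility Trial Design calls the study "unblinded and uncontrolled". Power Analysis and Missing Data Analysis sets a one-sided t-test at 0.025 against the average of two baseline evaluations, and gives no effect size, SD or sample size. No section describes masking the EEG reader to visit or reading files in shuffled order.

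**The concern.** The primary result is a within-patient change in a count. There is no concurrent arm to share a shift in how spikes are recognised, so a lower detection rate after treatment looks the same as suppression. Visual counting involves judgement about what qualifies as a spike. When files are read session by session in an openly treated cohort, that judgement can move with knowledge of the visit or simply with time.

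The second exposure is choice. Two counts of the same recording, with neither designated, allow the more favourable one to become the endpoint after both have been seen.

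This result decides whether a randomized trial follows. How the primary measurement is taken is also study conduct, which has to be settled before the recordings are read.

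**Working it through.** The protocol states no sample size, power or variance, so there is no figure to reproduce. The only stated inputs are the one-sided test and the 0.025 level. Everything else below is assumed.

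**Reading drift at one visit**

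- Assumed test: paired t-test on the log ratio of follow-up to baseline spike rate. The protocol says only that it is a one-sided t-test.
- Assumed true treatment effect: zero.
- Assumed drift: the reader counts a fraction d fewer spikes after treatment.
- Noncentrality: −ln(1 − d) × √n / SD.
- False-success rate: the probability that a noncentral t with n − 1 degrees of freedom exceeds the 97.5th percentile of the central t.

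Worked case, n = 20, SD 0.5, d = 10%: −ln(0.9) = 0.105. Then 0.105 / 0.5 × √20 = 0.94, the critical value on 19 degrees of freedom is 2.09, and the rejection probability is 14.4%.

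| SD of log ratio | n | d = 0 | d = 10% | d = 20% | Observed fall that reaches significance |
|---|---|---|---|---|---|
| 0.5 | 10 | 2.5% | 8.7% | 24.3% | 30.1% |
| 0.5 | 20 | 2.5% | 14.4% | 47.4% | 20.9% |
| 0.5 | 30 | 2.5% | 19.9% | 65.6% | 17.0% |
| 0.8 | 10 | 2.5% | 5.6% | 12.1% | 43.6% |
| 0.8 | 20 | 2.5% | 8.1% | 21.9% | 31.2% |
| 0.8 | 30 | 2.5% | 10.3% | 31.5% | 25.8% |

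The last column is 1 − exp(−t × SD / √n), taking the observed SD to equal the assumed one. A 10% drift therefore gives 5.6% to 19.9%, and a 20% drift 12.1% to 65.6%, against a nominal 2.5%.

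**Free choice between two counts, no drift**

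At a single visit, two tests at 0.025 cannot exceed 2 × 2.5% = 5% in total. If significance at any of the five follow-up visits is taken as success, a simulation of 10,000 runs (n = 20, SD 0.5, assumed correlation 0.5 between visits and 0.8 between counts) gives about 9.7% with one count and 14.5% with either. Choice of count adds the difference, 14.5 − 9.7 = 4.8 percentage points. The 9.7% comes from testing at five visits, which is a separate matter that naming or masking a count does not cure.

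**With one fixed count and no differential reading**

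The single-visit rate stays at 2.5%.

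**The case against.** The strongest reply is grammatical. The phrase "with the quantitation reported as a trial endpoint" directly follows the naming of Spike Beacon, while the human task is described as inspection, and the section covers both safety and counting. Inspection for safety and software for counting is a plausible intention. Under it, with fixed settings, human drift does not enter. This stands as a possible reading, but the text does not settle it, and that lack is the point.

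A reader might infer that the protocol has the endpoint read by someone who knows the visit. It does not say so. "unblinded and uncontrolled" describes the study, and review after each session is not a statement of what the reader knows. The supportable claim is that no masking is described.

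A reader might also infer that baseline recordings are counted by a different process, because the review sentence lists only treatment and follow-up sessions. The documents do not support that. Primary Endpoint and Study Success puts all phases on the same unit, and the review section compares later spike frequency with the baseline sessions. What is absent is only a commitment to the same reader, method and settings.

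Drift could also run upward, since the review is asked to flag increases. That would hide a real effect rather than create a false one. Even at 10% downward drift, 80% to 94% of null trials in the table still fail. Software settings and reading order often sit in a SAP or reading manual, and a feasibility study may not need an extensive statistical plan. Neither point covers a protocol that itself introduces two counts for its primary endpoint and leaves the choice open.

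**Conclusion.** The point holds as a gap in how the primary measurement is fixed, not as a demonstrated bias. The protocol names two counts, designates neither and describes no masked reading, while success rests on an uncontrolled fall in that count. Under the assumptions shown (log scale, paired test, n 10 to 30, SD 0.5 to 0.8, no true effect), a 10% fall in detection raises single-visit false success from 2.5% to about 6% to 20%. None of these inputs comes from the protocol, so the range illustrates sensitivity and does not estimate what will happen. The drift figures apply only if the endpoint is a visual or reader-edited count. The change is worth making before recordings are read, because it is cheap and the result decides whether a randomized trial follows.

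**What to change.** Keep the session-by-session visual review as it stands, for safety. In the endpoint section:

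- Name one primary count in advance. The Spike Beacon count is preferable, with version and settings locked and run in one batch on all baseline and follow-up files.
- Use resting segments of equal length, matched by waking or sleep stage. Baseline evaluations last two hours, while Table 2 gives 30 minutes of resting dEEG at follow-up unless a sleep recording is needed. Removing labels alone would therefore often not conceal the visit.
- If a human confirms detections, have the existing reader do so on those segments, with date and visit removed and in random order, after the safety reads are complete.
- Report the other count as a sensitivity analysis.

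The cost is a paragraph of wording, file preparation and, if detections are confirmed by a human, one re-read by the existing reader. No patients, visits or readers are added. Endpoint counts arrive later, the longer baseline recordings are only partly used, and masking is imperfect where the same person did the safety review. If the sponsor already intends the automated count, a sentence saying so and locking its settings for all files resolves most of the point.

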The short term effects of transcranial neuromodulation are typically assumed to be mediated by increasing or decreasing of cortical excitability. The longer term effects appear to reflect stable changes in cortical plasticity, including long term potentiation (LTP) and long term depression (LTD) as evidenced by learning effects that are mediated by NMDA (Monte-Silva et al., 2013). The rationale of the present interventions is that inducing long term depression in the epileptogenic zone will be effective in suppressing seizures. However, the scientific understanding of this manipulation is limited, such that there is risk of changing plasticity in ways that are unwanted or maladaptive.

Mitigating the Risk of Unwanted Plasticity

In addition to manipulating epileptiform activity, the GTEN treatment may change other aspects of the patient's cortical function that may create unwanted changes in brain function or plasticity. The large general literatures for tDCS and slow rTMS suggest there are unlikely to be serious unwanted changes. Nonetheless, we will achieve more focal and potentially more effective current delivery than in previous research with tDCS, and we will achieve deeper current delivery than previous research with slow rTMS.

The primary effect on the target brain region is expected to be the induction of long term depression. We will evaluate general cognitive function in each patient with scores on the California Verbal Learning Test, paying close attention to any changes from the expected improvement in performance with practice from the normative data. The patient's baseline performance with the CVLT is assessed during the pre-treatment baseline assessment. We will also review the Quality Of Life In Epilepsy ratings and the seizure diary with each patient and family, systematically reviewing any complaints or reports that may suggest the treatment is creating unwanted changes in brain function. Finally, for each patient we will examine the effective dose delivered to non target brain regions as a function of the DCSV targeting recorded by the GTEN Planning Module to insure that the electrical dosage (and the presumed induction of long term depression) is appropriately limited to the target cortex.

Pre-Clinical Testing with Normal Volunteers

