- (3) A history or condition of status epilepticus or psychogenic seizures.

- (4) Presence of a cardiac pacemaker, vagus nerve stimulator, or metal implantation in the body (other than the teeth) including neurostimulators, cochlear implants, and implanted medication pumps.
- (5) Previous surgery involving opening the skull.
- (6) Allergy to or condition contraindicating lidocaine.
- (7) Unable to express presence of pain or discomfort.

Escape Criteria

For individual patients, the study will be terminated for any of the following reasons:

- (1) Unacceptable discomfort or pain at stimulation currents of 200 μ A.
- (2) A tonic-clonic seizure occurring during a stimulation session.
- (3) Emergence of a first-in-life tonic-clonic seizure at any time during the study.
- (4) Status epilepticus.
- (5) A two-fold increase of seizure frequency over the baseline seizure frequency. If the frequency of seizures is very low, then an apparent increase during treatment (not reliably quantified as a two-fold increase) will be discussed with the patient, family, physician and Study committee.

The entire study will terminate if 5 subjects meet escape criteria.

Baseline Evaluation

During a one-month pre-treatment baseline evaluation period, the patient (and/or family) will maintain the seizure diary, which will be reviewed by the study coordinator in a phone contact once per week. In addition, two two-hour routine dEEG evaluations will be conducted in the baseline evaluation period, including the opportunity for sleep for patients who may have interictal events in sleep or drowsiness. Each baseline evaluation also includes the California Verbal Learning Test, and the Quality of Life in Epilepsy report.

Probe Treatment and Evaluation

The GTEN Plan is developed to apply current pulses to the epileptic focus, as it is identified from the dEEG source localization of the spike onset. The GTEN Plan will often include more than one treatment option, primarily depending on the orientation of the cortical region identified as the epileptic focus. To evaluate a treatment targeting option, a probe treatment may be conducted, consisting of one 17-min pulsed treatment block (Figure 10) followed by one hour of dEEG evaluation and spike counting. If multiple targeting options are evaluated, the one with the best evidence of spike suppression will be selected for the 5 session treatment intervention.

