The probe treatment and evaluation protocol is thus a subset (one block instead of 3 blocks of 17-minute pulses) of the approved treatment protocol.

The same GTEN Planning Module is used to develop each probe treatment targeting plan, with the primary difference being the cortical region that is targeted. This is a judgment made by the scientists (Drs. [name] and [name] at EGI) on the basis of the ability to target the cortical region, which is very difficult in medial temporal regions, and the epileptologist ([name] at Harborview) on the basis of the likely relation of the spike development to seizure onset. Often there are multiple possible targets, and the probe treatments and evaluations may allow us to contrast their efficacies.

Treatment Protocol

A two hour GTEN treatment session then targets the identified focal epileptogenic zone for 5 days during one week. For the first ten patients the post treatment monitoring is continued for 3 hours after the treatment session. For those patients whose spikes were more frequent during sleep during the baseline evaluation sessions, an effort will be made to have them fall asleep as the lidocaine takes effect and before the GTEN treatment begins, so that the treatment matches the excitable state during which spikes occur.

All sessions are conducted by personnel who are trained in the dEEG and GTEN 100 operation, including the ability to recognize epileptiform discharges in the dEEG signals. At least one person on the research staff at each session will be certified in first aid in the case that a seizure occurs. The epileptologist at each trial site will provide medical supervision, including recognition of possible adverse events and decision to terminate treatment.

Follow up Protocol

The one week treatment period is followed by a weekly seizure diary review by phone with the study coordinator for six months, plus a dEEG follow up evaluation session in weeks 2, 4, 8, 16, and 24. Each follow up session includes dEEG evaluation during the entire session, including during the review of seizure diary, cognitive function testing with the California Verbal Learning Test, and the Quality of Life in Epilepsy report, as well as a resting dEEG interval. If the patient has interictal events in sleep or drowsiness, the resting dEEG evaluation will include a quiet period for a nap.

Primary Endpoint and Study Success

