First Treatment Session	
 • Review of seizure diary. • Application of the Geodesic Sensor Net. • Geodesic Photogrammetry System (GPS) to localize sensors. • bEIT scan to verify electrical head model. Lidocaine iontophoresis conditioning during this scan. • 10 minutes resting dEEG. • GTEN treatment: 3 sets of 500 pulses (600s intervals between sets) or 3 sets of sustained tDCS with the same intervals. • 30 minutes resting dEEG (unless sleep EEG needed, then 2 hrs). • California Verbal Learning Test • Quality of Life Questionnaire
Treatment Sessions 2-5	
 • Review of seizure diary. • Application of the Geodesic Sensor Net. • Geodesic Photogrammetry System to localize sensors. • 10 minutes resting dEEG. Lidocaine iontophoresis conditioning during this time. • GTEN treatment, 3 sets of 500 pulses (600s intervals between sets) or 3 sets of sustained tDCS with the same intervals. • 30 minutes resting dEEG (unless sleep EEG needed, then 2 hrs). • California Verbal Learning Test • Quality of Life Questionnaire
Follow up routine dEEG, weeks 2, 4, 8, 16, and 24.	
 • Review of seizure diary. • Application of the Geodesic Sensor Net. • Geodesic Photogrammetry System to localize sensors. • 30 minutes resting dEEG (unless sleep EEG needed, then 2 hrs). • California Verbal Learning Test • Quality of Life Questionnaire

Table 2. Summary of treatments and assessments.

Bibliography

- Bae, E. H., Schrader, L. M., Machii, K., Alonso-Alonso, M., Riviello, J. J., Jr., PascualLeone, A., & Rotenberg, A. (2007). Safety and tolerability of repetitive transcranial magnetic stimulation in patients with epilepsy: a review of the literature. *Epilepsy & behavior : E&B*, 10(4), 521-528. doi: 10.1016/j.yebeh.2007.03.004

- Bergey, G. K. (2013). Neurostimulation in the treatment of epilepsy. *Exp Neurol*, 244, 87-95. doi: 10.1016/j.expneurol.2013.04.004
- Bertram, E. (2007). The relevance of kindling for human epilepsy. *Epilepsia*, 48 Suppl 2, 65-74.

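### Table 2 omits the baseline memory test and quality-of-life form that the text requires, and adds five treatment-week memory tests that confound an endpoint defined as gain beyond practice

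*Protocol*

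**What the plan says.** **Baseline, in the text.** Under Baseline Evaluation, "two two-hour routine dEEG evaluations will be conducted in the baseline evaluation period", and "Each baseline evaluation also includes the California Verbal Learning Test, and the Quality of Life in Epilepsy report". The section on mitigating unwanted plasticity agrees for the CVLT: "The patient's baseline performance with the CVLT is assessed during the pre-treatment baseline assessment".

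**Baseline, in Table 2.** The Pre-Treatment Evaluation row lists weekly diary review, MRI when available, and this: "Two routine dEEG evaluations to capture epileptiform discharges (ED), including spikes and seizures". Neither the CVLT nor the QOLIE appears. Every other row of the table names both. The protocol introduces Table 2 as the summary of procedures for each patient session, and the only exception it states is longer EEG monitoring in the first ten patients.

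**Treatment week.** Treatment Protocol says that GTEN "targets the identified focal epileptogenic zone for 5 days during one week" and does not mention cognitive or quality-of-life testing. In Table 2 the rows for the first treatment session and for sessions 2-5 both close with "30 minutes resting dEEG (unless sleep EEG needed, then 2 hrs). • California Verbal Learning Test • Quality of Life Questionnaire", listed after the stimulation sets.

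**Follow-up.** Follow up Protocol gives weekly diary calls, "plus a dEEG follow up evaluation session in weeks 2, 4, 8, 16, and 24", with both instruments at each session. Table 2 uses the same weeks. Monitoring of Risk schedules the same instruments weekly for three weeks after treatment and then at week 8.

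**Use of the scores.** Secondary Endpoints and Study Success defines the cognitive endpoint as improvement over and above practice, with practice estimated from norms and from a sham control group. The quality-of-life endpoint is any improvement in ratings. The unwanted-plasticity section uses the CVLT as a safety check, "paying close attention to any changes from the expected improvement in performance with practice from the normative data". Clinical Feasibility Trial Design describes the study as open-label and uncontrolled.

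**The concern.** Two separate things go wrong, and both arise from the visit schedule.

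First, the table and the text disagree on whether the two instruments are given before treatment. Site staff commonly work from the schedule table. A site that did so here would take its first CVLT and QOLIE at the end of the first treatment day. A pre-treatment score that was never collected cannot be recovered in the analysis.

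Second, the CVLT is a learning test, and the protocol itself expects scores to rise with repetition. Table 2 places five further administrations, all within one week, between baseline and the first follow-up visit. Both uses of the CVLT depend on knowing how much practice alone would add. If practice is under-corrected, apparent benefit is inflated. In the other direction, extra practice can offset a real memory decline, which is the signal the unwanted-plasticity section relies on this test to detect.

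**Working it through.** There is no sample size, power or error-rate figure to reproduce on this point. The check is a count of administrations and a reading of what the correction needs.

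**Inputs**
- Baseline administrations: 2 by the Baseline Evaluation text; 0 by Table 2.
- Treatment-week administrations: 5 by Table 2 (first session, plus sessions 2-5).
- Follow-up administrations: 5 by Follow up Protocol and Table 2 (weeks 2, 4, 8, 16, 24); 4 by Monitoring of Risk (three weekly, then week 8).

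**Counts** (total = baseline + treatment week + follow-up)

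| Reading | Total | Before first follow-up |
|---|---|---|
| Table 2 alone | 0 + 5 + 5 = 10 | 0 + 5 = 5, none pre-treatment |
| Text baseline plus Table 2 | 2 + 5 + 5 = 12 | 2 + 5 = 7 |
| Text baseline, Table 2 treatment week, Monitoring of Risk follow-up | 2 + 5 + 4 = 11 | 2 + 5 = 7 |
| Text baseline, no treatment-week tests, follow-up as in Table 2 | 2 + 0 + 5 = 7 | 2 + 0 = 2 |

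So with the baseline tests done as the text requires, seven exposures precede the first follow-up whichever follow-up schedule applies. Five of the seven come from the treatment-week rows.

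**What the correction needs.** Let g(k) be the mean practice gain in the CVLT after k earlier administrations, T the treatment effect, and c the practice correction applied. The corrected week-2 change then estimates

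T + g(7) − c with the treatment-week tests, and

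T + g(2) − c without them.

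The treatment-week tests therefore add g(7) − g(2) to what c has to absorb. The protocol names two sources for c:
- Norms. The protocol does not say that its norms cover seven exposures with five inside one week.
- A sham control group. This study has none.

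The term g(7) − g(2) is neither measured within the trial nor supplied from outside it. The same term enters the safety check: if T is negative, an uncorrected positive practice term moves the observed change towards zero or above it.

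**What cannot be computed.** The document gives no practice gain per administration, no CVLT standard deviation, no ceiling and no sample size. It also does not state which test form is used at which visit, and alternate forms would change g. The direction follows from the protocol's own expectation of practice gains; the size does not.

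**QOLIE.** The counts are the same, but the protocol gives no reason why filling in a rating form would raise later ratings. The formula above has no counterpart for it. What remains is its absence from the pre-treatment row.

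**The case against.** The strongest reply is that the governing text already settles the baseline. Two sections place the CVLT before treatment and one places the QOLIE there; Table 2 is only an overview. That is correct. A reader might infer from the table that the endpoints have no clean baseline, and the documents do not support that. What stands is a contradiction that puts the baseline at risk at any site following the table.

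The treatment-day tests may also be deliberate. The summary of consent-form changes says the form describes baseline, treatment and evaluation sessions including both instruments, and a treatment-week cognitive check has a plausible safety purpose. The Treatment Protocol text is silent rather than contrary. This also stands, so the treatment-week entries cannot simply be called a table error. But if they are intended, the extra practice is part of the design and the endpoint has to allow for it.

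A reader might go further and say that daily re-testing swamps the cognitive result, or attach a number of words to it. Nothing in the document supports a figure, and multiplying an assumed gain per test by five would also assume that gains never level off.

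Finally, an uncontrolled study cannot attribute a gain to treatment in any case. That is true, and removing the treatment-week tests does not cure it. It does remove five of the seven exposures that the practice correction would otherwise have to cover.

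**Conclusion.** The point holds in this form. Table 2 contradicts Baseline Evaluation by leaving the CVLT and QOLIE out of the pre-treatment row. It also schedules five treatment-week CVLT administrations, bringing the exposures before week 2 from 2 to 7. With no control group and no sham group, the protocol has no stated means of separating that practice from treatment, for the cognitive endpoint or for the cognitive safety check. The size of the bias is unknown.

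The conclusion rests on two assumptions: that the order of items in Table 2 follows the order of the session, so that the treatment-day tests come after stimulation; and that repeating the CVLT produces carry-over, which the protocol itself expects. It does not extend to a claim that quality-of-life ratings are biased by repetition.

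The affected items are secondary endpoints and one stated safety check. The primary endpoint, spike suppression, is untouched. The change should be made, but trial success does not depend on it.

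**What to change.** 1. Add the CVLT and QOLIE to the Pre-Treatment Evaluation row of Table 2, at both baseline evaluations, to match the text.
2. Remove the CVLT from the rows for treatment sessions 1-5. If a treatment-week cognitive check is wanted for safety, use different test material and state that it does not enter the endpoint.
3. Define the cognitive and quality-of-life endpoints as change from the pre-treatment scores to the follow-up visits.
4. Reconcile the follow-up schedule in Monitoring of Risk (weekly for three weeks, then week 8) with weeks 2, 4, 8, 16 and 24 in Follow up Protocol and Table 2.
5. Delete the reference to a sham control group as a source of the practice correction, since this study has none.

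The cost is a table correction and a few sentences of text; the treatment visits become shorter if no substitute check is added. The downside is that no CVLT score comparable with the endpoint is available on treatment days. The study remains uncontrolled, so any cognitive gain should still be reported as descriptive.
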